7.3.2 Visit V4 (week 2, a phone interview)

- Review SMBG and glycemic control record
- Assess AEs and potential DKA and record concomitant medications
- Schedule an unscheduled clinic visit if clinically indicated

7.3.3 Visit V5 (week 6)

- Review SMBG and glycemic control record
- Measure vital signs, including blood pressures and heart rate
- Measure body weight
- Draw blood from subjects who have completed a compliant fast as described in [Section 6.7.2.1](#). The specific laboratory tests scheduled for this visit are listed in [Appendix 2](#)
- Collect a clean catch mid-stream urine sample for urinalysis in all subjects and for UPT for women of child bearing potential
- Assess AEs and potential DKA and record concomitant medications.
- Collect blood specimens for sparse PK sampling from selected subjects in participating centers

7.3.4 Visit V6 (week 12)

- Perform an abbreviated physical examination
- Review SMBG and glycemic control record
- Measure vital signs, including blood pressures and heart rate
- Measure body weight
- Draw blood from subjects who have completed a compliant fast as described in [Section 6.7.2.1](#). The specific laboratory tests scheduled for this visit are listed in [Appendix 2](#)
- Collect a clean catch mid-stream urine sample for urinalysis in all subjects and for UPT for women of child bearing potential
- Dispense study medication
- Assess AEs and potential DKA, and record concomitant medications.
- Collect blood specimens for sparse PK sampling from selected subjects in participating centers

7.3.5 Visit V7 (week 18, a phone interview)

- Review daily SMBG and glycemic control record
- Assess AEs, potential DKA, and record concomitant medications
- Schedule an ad hoc visit if clinically indicated

7.3.6 Visit V8 (week 24)

- Review SMBG and glycemic control record
- Perform an abbreviated physical examination
- Measure vital signs, including blood pressures and heart rate
- Measure body weight
- Perform 12-lead ECG
- Draw blood from subjects who have completed a compliant fast as described in [Section 6.7.2.1](#). The specific laboratory tests scheduled for this visit are listed in [Appendix 2](#)
- Collect a clean catch mid-stream urine sample for urinalysis in all subjects and for UPT for women of child bearing potential;
- Dispense investigational product
- Assess AEs, potential DKA, and record concomitant medications

7.3.7 Visit V9 (week 36)

- Review SMBG and glycemic control record
- Perform an abbreviated physical examination
- Measure vital signs, including blood pressures and heart rate
- Measure body weight

- Draw blood from subjects who have completed a compliant fast as described in [Section 6.7.2.1](#). The specific laboratory tests scheduled for this visit are listed in [Appendix 2](#)
- Collect a clean catch mid-stream urine sample for urinalysis in all subjects and for UPT for women of child bearing potential;
- Dispense investigational product
- Assess AEs, potential DKA, and record concomitant medications

7.3.8 Visit V10 (week 48)

- Review SMBG and glycemic control record
- Perform an abbreviated physical examination
- Measure vital signs, including blood pressures and heart rate
- Measure body weight
- Perform 12-lead ECG
- Draw blood from subjects who have completed a compliant fast as described in [Section 6.7.2.1](#). The specific laboratory tests scheduled for this visit are listed in [Appendix 2](#)
- Collect a clean catch mid-stream urine sample for urinalysis in all subjects and for UPT for women of child bearing potential;
- Dispense investigational product
- Assess AEs, potential DKA, and record concomitant medications

7.3.9 Visit V11, V13, V15, V17, etc. (week 60 to end of treatment; phone interviews)

- Review daily SMBG and glycemic control record
- Assess AEs, potential DKA, and record concomitant medications
- Schedule an ad hoc visit if clinically indicated

7.3.10 Visits V12, V14, V16, V18, etc. (week 72 to end of treatment, clinic visits)

- Review SMBG and glycemic control record
- Perform an abbreviated physical examination
- Measure body weight
- Measure vital signs, including blood pressures and heart rate
- Perform 12-lead ECG
- Draw blood from subjects who have completed a compliant fast as described in [Section 6.7.2.1](#). The specific laboratory tests scheduled for this visit are listed in [Appendix 2](#)
- Collect a clean catch mid-stream urine sample for urinalysis in all subjects and for UPT for women of child bearing potential
- Dispense study medication
- Assess AEs, potential DKA, and record concomitant medications

7.3.11 Visit EV (end of treatment, a clinic visit)

An End of Treatment Visit should be scheduled within 2 weeks after the end of treatment is declared or as soon as scheduling allows.

- Review SMBG and glycemic control record
- Perform an abbreviated physical examination
- Measure body weight
- Measure vital signs, including blood pressures and heart rate
- Perform 12-lead ECG
- Draw blood from subjects who have completed a compliant fast as described in [Section 6.7.2.1](#). The specific laboratory tests scheduled for this visit are listed in [Appendix 2](#)
- Collect a clean catch mid-stream urine sample for urinalysis in all subjects and for UPT for women of child bearing potential
- Perform the drug accountability procedure and record the last day of dose administration
- Assess AEs, potential DKA, and record concomitant medications

7.4 Exit Visit

7.4.1 Visit FU (4 weeks after the last dose of investigational product is administered or if a subject withdraws consent)

- Review SMBG and glycemic control record
- Perform a complete physical examination
- Measure vital signs, including blood pressures and heart rate
- Measure body weight
- Perform 12-lead ECG if clinically indicated
- Draw blood from subjects who have completed a compliant fast as described in [Section 6.7.2.1](#). The specific laboratory tests scheduled for this visit are listed in [Appendix 2](#)
- Collect a clean-catch, mid-stream urine sample for urinalysis in all subjects and for UPT for women of child bearing potential
- Assess AEs, potential DKA, and record concomitant medications: If a subject has an ongoing SAE, the subject will be followed until the AE has resolved or no meaningful further improvement can be expected. Every possible attempt should be made to document resolution of acute and chronic toxicities.

7.5 Discontinuation of Investigational Product Administration

Subjects who discontinue the investigational product administration early but are willing to remain in the study to allow safety information to be collected should complete the End of Treatment visit procedures. Safety data may be documented following the scheduled clinic visit and/or phone interview procedures as much as possible without the study drug

dispensation and accountability procedures. Alternative follow up methods to allow safety assessment to be recorded may be implemented as unscheduled visits.

7.6 Early Termination Procedures

Subjects who withdraw consent and have received investigational product should have a follow-up examination, including a complete physical examination, vital signs, ECG, and clinical laboratory tests (hematology, serum chemistry, and glycemic control). The sponsor must be notified in the event that a subject withdraws or has been withdrawn from the study.

8 QUALITY CONTROL AND ASSURANCE

The clinical research facility will be monitored by the study monitor to ensure correct performance of the study procedures and to ensure that the study is conducted according to the protocol and relevant regulatory requirements. CRF entries will be verified with the source documentation.

Quality control principles will be applied throughout the performance of this study by following the Standard Operating Procedures (SOP) of the CRO and the sponsor. Review procedures will be implemented at the CRO for all documents that are generated in relation to the study.

9 PLANNED STATISTICAL METHODS

9.1 General Considerations

The following sections provide a summary of the planned analysis of the trial but a full analysis plan will be developed as a separate document and will become the final plan. All statistical analyses will be performed using SAS Version 9.4 or higher.

Data summaries will use descriptive statistics (number of subjects [N], mean, standard deviation [SD], Q1, median, Q3, minimum, and maximum) for continuous variables, and frequency and percentage of subjects for categorical and ordinal variables. If there are missing values, the number missing will be presented, but without a percentage.

Unless otherwise specified, all tests will be two-tailed using a 0.05 level of significance. All confidence intervals (CIs) will be two-sided 95% confidence intervals.

9.2 Determination of Sample Size

The sample size is determined based on the required number of MACE+ for the program-wide meta-analysis of bexagliflozin cardiovascular safety assessment, where non-inferiority of bexagliflozin to control will be formally assessed from a hazard ratio perspective. There will be no formal non-inferiority statistical testing of MACE+ rate within THR-1442-C-476; the only primary endpoint is the change in HbA1c from baseline to Week 24.

The following are the assumptions for protocol THR-1442-C-476 to have an adequate number of events to appropriately power the meta-analysis:

1. Enrollment will take 1 year.
2. Every subject is followed for a minimum of 1 years and a maximum of 3 years, except for premature withdrawals.
3. The annual premature withdrawal rate is 6.5%
4. The randomization ratio is 2:1 (bexagliflozin vs. placebo)
5. The primary analysis is non-inferiority of treatment vs. placebo from a hazard ratio perspective over a 3 year period, using a non-inferiority margin of 1.8 for MACE+.
6. A one-sided 0.025 level of significance will be used to assess non-inferiority
7. Non-inferiority to placebo for MACE + will be assessed by comparing the upper limit of a one-sided 97.5% CI of the hazard ratio (treatment vs. placebo) to a margin of 1.8; the hazard ratio will be calculated from Cox proportional hazards regression.
8. The actual hazard ratio is an equivalence hazard ratio of 1.00 and the reference group monthly hazard rate is 0.00308.

Under the above assumptions, 134 events across 1650 randomized patients (1100 vs. 550 placebo) yields 87% power to detect non-inferiority of experimental treatment to placebo with respect to MACE+. Thus, protocol C-476 will continue until at least 134 events have occurred. If the study accrues 134 MACE+ events before every subject has either been exposed to investigational product for at least 52 weeks or withdrawn from the study, the

study will continue until all subjects either complete the minimum 52 week course of exposure or withdraw.

If the true hazard ratio is 0.9, the power to claim non-inferiority increases to 93%. This should yield sufficient power for the meta-analysis (where all experimental dose groups are pooled and considered as one treatment group), since the number of patients with events in the meta-analysis will be at least the same as that in protocol THR-1442-C-476 and since the treatment to placebo ratio will remain approximately 2:1 across the meta-analysis.

To determine the sample size of THR-1442-C-476 study, the event rates were estimated based on published cardiovascular outcome study SAVOR (Scirica et al., 2013; Scirica et al., 2014a). In the study, subjects with T2DM with a baseline HbA1c of 6.5% to 12.0%, and either a history of established cardiovascular disease or multiple risk factors for vascular disease were included. The estimated 2 year event rate of the placebo group was 7.2%. Assuming a similar event rate in the THR-1442-C-476 study, a sample size of 1650 is planned so that 134 study subjects with an adjudicated MACE+ will occur with a treatment duration between 2 and 3 years. The estimated numbers of MACE+ based on the heart failure background were shown in Table 2. The projected number of CV deaths from subjects with HF history is anticipated to be ≤50% of the total CV deaths.

Table 2. Estimated Event Rates in Patients with Cardiovascular Risks¹

Event rate in 2 years	No prior HF (%)	Prior HF (%)	From 1250 non-HF	From 400 HF	Total of 1650 subjects
Mortality	3.5%	8.8%	44	35	79
CV death	2.3%	7.3%	29	29	58
MI	3.2%	4.5%	40	18	58
Stroke		1.0%		16	16
Hospital. for HF	1.7%	10.2%	21	41	62
Hospital. for unstable angina		1.0%		16	16

¹ Event rate is based on the outcome of the placebo group in the SAVOR study (Scirica et al., 2013; Scirica et al., 2014a)

The estimated sample size of 1650 in a 2:1 active to placebo ratio will yield 90% power to detect a treatment effect of 0.22% in HbA1c reduction assuming the SD is 1.1% and HbA1c values from all subjects will be used for the primary efficacy analysis.

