9.5.2 Handling Dropouts, and Missing Data

Discontinuation criteria are explained in [Section 6.13](#). Subjects who withdraw consent to participate in the study will not be replaced.

The early termination rate is estimated to be 6.5% annually. To the extent possible, attempts will be made to minimize the amount of missing data through measures planned in the study conduct. But if data are missing for the primary endpoint and the first key secondary endpoint (ie, change of HbA1c for subjects who have been prescribed insulin), they will be handled as follows:

1. All observed data will be analyzed and data obtained after rescue will not be excluded and considered as missing. This will be considered the primary analysis.
2. Missing primary efficacy endpoint information will be imputed via multiple imputation linear regression approach. A total of 10 imputed datasets will be generated, and the corresponding primary analyses will be carried out on each imputed dataset for each endpoint; the analyses results will be combined across the 10 datasets using the standard techniques for multiply imputed data sets in order to yield overall treatment comparison results on the imputed data for each endpoint.

The number, timing, pattern, reason for and possible implications of missing values in efficacy assessments will be investigated. The dropout patterns will be assessed by Kaplan-Meier plots if applicable to assess whether they differ between treatment groups.

The handling of missing safety endpoint (MACE+) data is described below in section 9.6.3; however, analyses on MACE+, while being collected in C-476, will only be formally analyzed in the meta-analysis.

For all other endpoints, the missing data will not be imputed and only the observed data will be used in the analyses.

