9.6 Secondary Endpoints

9.6.1 Key Secondary Efficacy Endpoints

The key secondary efficacy endpoints include:

- Change in HbA1c from baseline to week 24 in randomized subjects who have been prescribed insulin to control their diabetes
- Change in body weight from baseline to week 48 in subjects with a BMI ≥ 25 kg/m²
- Change in SBP from baseline to week 24 in subjects with baseline systolic blood pressure ≥ 140 mmHg

It is anticipated that approximately 50% of the randomized subjects will have been prescribed insulin to manage their disease. The sample size for the key secondary efficacy end point to evaluate the treatment effect of bexagliflozin compared to placebo on the change in HbA1c from baseline to week 24 in subjects who have been prescribed insulin to control their diabetes is estimated to be 800. For this key secondary endpoint, the estimated sample size will yield >90% power to detect a treatment effect of 0.3% assuming the SD is 1.1% for a two-sided superiority testing.

It is also anticipated that a high proportion of the randomized subjects would have a baseline BMI ≥ 25 kg/m² and baseline SBP ≥ 140 mmHg in this cardiovascular risk enriched population for the analysis in change in body weight and change in SBP.

A hierarchical testing procedure will be applied to these endpoints in the sequence provided above. These key secondary endpoints will only be tested sequentially when significant treatment differences are established for the primary efficacy endpoint in the comparisons between bexagliflozin and placebo.

The comparison between treatment populations at week 24 (HbA1c and SBP) or 48 (body weight) will be carried out using an MMRM ANCOVA model with unstructured covariance assumption. The model will include terms for treatment, randomization stratification factors, visit, and treatment-by-visit interaction as fixed effects and the corresponding baseline value as an additional fixed effect covariate. Treatment comparison p-values and the difference at week 24 (HbA1c and SBP) or 48 (body weight) will be estimated from the model, with the two-sided 95 % CIs of the difference also presented. If the model does not converge with the unstructured correlation assumption, an autoregressive (1) covariance structure will be used.

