To determine the sample size of THR-1442-C-476 study, the event rates were estimated based on a published cardiovascular outcome study (SAVOR; Scirica et al., 2013; Scirica et al., 2014a). In the SAVOR study, subjects with T2DM with a baseline HbA_{1c} of 6.5% to 12.0%, and either a history of established cardiovascular disease or multiple risk factors for vascular disease were included. The estimated 2 year event rate of the placebo group was 7.2%. Assuming a similar event rate in the THR-1442-C-476 study, a sample size of 1650 is anticipated to provide 134 MACE+ within a treatment duration of between 2 and 3 years. The estimated numbers of MACE+ based on the heart failure background are shown in **Table 1**. The projected number of CV deaths from subjects with an HF history is anticipated to be ≤50% of the total CV deaths.

Table 1 Estimated Event Rates in Patients with Cardiovascular Risks¹

Event rate in 2 years	No prior HF (%)	Prior HF (%)	From 1250 non-HF	From 400 HF	Total of 1650 subjects
Mortality	3.5%	8.8%	44	35	79
CV death	2.3%	7.3%	29	29	58
Myocardial infarction	3.2%	4.5%	40	18	58
Stroke		1.0%	16		16
Hospital. for HF	1.7%	10.2%	21	41	62
Hospital. for unstable angina		1.0%	16		16

¹ Event rate is based on the rate observed for the placebo group in the SAVOR study (Scirica et al., 2013; Scirica et al., 2014a)

The estimated sample size of 1650 in a 2:1 active to placebo ratio yields 90% power to detect a treatment effect of 0.22% in HbA_{1c} reduction assuming the SD is 1.1% and HbA_{1c} values from all subjects will be used for the primary efficacy analysis.

For the key secondary objective to measure change in HbA_{1c} from baseline to week 24 in randomized subjects who have been prescribed insulin to control their diabetes, it is anticipated that approximately 50% of the randomized subjects will have been prescribed insulin to manage their disease. For this key secondary endpoint, a sample size of 800 subjects will yield >90% power to detect a treatment effect of 0.3% assuming the SD is 1.1% for a superiority testing at one sided significance level of 0.025.

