6. GENERAL ASPECTS FOR STATISTICAL ANALYSIS

6.1. GENERAL METHODS

The proposed statistical methodology and analyses are in accordance with the principles outlined by the ICH E9 guidelines. All statistical analyses will be conducted using SAS statistical software version 9.3 or higher.

Tables, listings and figures (TLFs) will be produced in accordance with the principles outlined by the ICH E3 guidelines. For most summary statistics, data will be analyzed by the following treatment arms: Bexagliflozin 20 mg and Placebo. All available data from subjects who signed an informed consent will be presented in the subject listings.

Data summaries will use descriptive statistics (number of subjects [n], mean, standard deviation [SD], Q1, median, Q3, minimum and maximum) for continuous variables, and frequency and percentage of subjects for categorical and ordinal variables, unless otherwise specified.

Unless otherwise specified, all statistical tests will be one-tailed using a 0.025 level of significance. All confidence intervals (CIs) will be two-sided 95% CIs.

The analysis visit window will be assigned to data collection. One selected data point per visit will appear in summary tables and figures. Refer to section 6.4 for details. All visit assessment data will be included in shift tables and will appear in the subject listings.

No data imputation will be applied for missing values, unless otherwise specified.

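### The stated 90% power for the primary HbA1c comparison works out at about 97% on the plan's own inputs, in both the protocol and the SAP

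*Combined protocol and SAP*

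**What the plan says.** The last paragraph of protocol 9.2 gives the only numerical power statement for the primary endpoint: 1650 subjects in a 2:1 "ratio will yield 90% power to detect a treatment effect of 0.22% in HbA1c reduction assuming the SD is 1.1" percent. The same sentence adds that "HbA1c values from all subjects will be used for the primary efficacy analysis". SAP 3.7 carries the claim over: the 2:1 "ratio yields 90% power to detect a treatment effect of 0.22" percent, with the same SD and the same use of all subjects.

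The remaining inputs stand elsewhere:

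- **Arm sizes**, protocol 9.2: "134 events across 1650 randomized patients (1100 vs. 550 placebo").
- **Alpha in the protocol**, section 9.1: "all tests will be two-tailed using a 0.05 level of significance". The synopsis confirms two-sided 0.05 for the primary endpoint.
- **Alpha in the SAP**, section 6.1: "all statistical tests will be one-tailed using a 0.025 level of significance".
- **Attrition**, protocol 9.5.2, repeated in SAP 8.1.2: "The early termination rate is estimated to be 6.5% annually".

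For the insulin-treated subset (about 800 subjects), protocol 9.6.1 words its power claim differently: "the estimated sample size will yield >90% power to detect a treatment effect of 0.3% assuming the SD is 1.1" percent. SAP 3.7 also uses the greater-than sign for that subset.

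**The concern.** The power sentence has every input it needs for a two-sample comparison of means, and the inputs do not give the result. Change in HbA1c at week 24 is the only primary endpoint, and the synopsis claim of adequate power for it has no other numerical support.

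As written, a reader cannot tell which of three things happened: the power figure is wrong, the detectable difference is wrong, or an SD or missing-data allowance was used and not reported. The third would matter most, because an allowance large enough to explain 90% would conflict with the attrition rate used elsewhere in the plan.

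**Working it through.** **Inputs.** n = 1100 and 550; difference 0.22%; SD 1.1%; critical value 1.960, which is the same for two-sided 0.05 and one-sided 0.025; no attrition, as the sentence specifies.

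**Step 1: try to reproduce the plan's 90%.**

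SE = SD × √(1/n₁ + 1/n₂) = 1.1 × √(1/1100 + 1/550) = 1.1 × 0.05222 = 0.05745

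Difference / SE = 0.22 / 0.05745 = 3.83

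Power = Φ(3.83 − 1.96) = Φ(1.87) = 96.9%

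The noncentral t distribution with 1648 degrees of freedom also gives 96.9%. The stated 90% is not reproduced. Type II error is 3.1% rather than 10%.

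**Step 2: allow for attrition.** Applying the stated rate to 24 weeks gives 1 − 0.935^(24/52) = 3.1%. Treating this as the share without a week-24 value is an assumption, since early termination and a missing HbA1c value are not the same thing, so a range is shown. An equal share is removed from each arm (normal approximation):

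| Share missing at week 24 | Power |
|---|---|
| 0% | 96.9% |
| 3% | 96.5% |
| 6.5% (a full year's loss) | 95.9% |
| 10% | 95.3% |
| 20% | 92.9% |
| 25% | 91.3% |
| about 28% | about 90% |
| 30% | 89.3% |

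**Step 3: solve for what would give 90%.** The multiplier is 1.960 + 1.282 = 3.242.

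- Difference, at N = 1650 and SD 1.1%: 3.242 × 0.05745 = 0.186%. The stated 0.22% is 0.22/0.186 = 1.18 times this.
- SD, at N = 1650 and 0.22%: 0.22 / (3.242 × 0.05222) = 1.30%.
- Total N, at 0.22% and SD 1.1%: about 1185 (790 and 395), which is 1 − 1185/1650 = 28% fewer than planned.
- Alpha, all else as stated: 3.83 − 1.28 = 2.55, a two-sided level of about 0.011.

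**Step 4: try other readings of the design.** Equal arms of 825 give 98.2%. One-sided 0.05 gives 98.6%, and two-sided 0.025 gives 94.4%. An SD inflated by √2 gives 77.3%. Two readings come close to 90%: 550 per arm (91.3%) and two-sided alpha 0.01 (89.5%). The first contradicts both the 1650 and the 2:1 in the sentence; the second appears nowhere in either document.

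**Step 5: apply the same method to the insulin subset.** With 800 subjects at 2:1, SE = 1.1 × √(1/533.3 + 1/266.7) = 0.0825; 0.3 / 0.0825 = 3.64; power = Φ(1.68) = 95.3%. That agrees with the plan's greater-than-90% claim, so the method fits the plan's other HbA1c power statement.

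**The case against.** There are four arguments on the other side.

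**The sentence could mean at least 90%.** A design with 97% power does deliver 90%, so the sentence is not false as a guarantee. But the plan uses a greater-than sign when it means a lower bound, and SAP 3.7 sets the two forms in adjacent paragraphs. A difference of 0.22% also reads like a value solved for, not a floor. This reading is possible but weak.

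**The calculation imports inputs and simplifies the analysis.** The power sentence names no alpha, test or completeness rate. The SAP's primary analysis is now multiple imputation followed by MMRM (SAP 8.1.1), not a two-sample comparison. So 97% is approximate, and the 3% missing at week 24 is an assumption. Neither point recovers 90%. If 1.1% is an unadjusted SD, adjustment for baseline would tend to raise power.

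**Nothing depends on it.** This stands. Both documents set the sample size by MACE+ events, the error understates power, and the synopsis claim of adequate power remains true.

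**A protocol text change is not free.** This also stands in part. Under protocol 10.2 any amendment needs ethics approval, which is out of proportion for this sentence alone.

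**Conclusion.** The concern holds. On the stated inputs, power for the primary comparison is 96.9%, not 90%, in both protocol 9.2 and SAP 3.7. Equivalently, the difference detectable with 90% power is about 0.186%, not 0.22%. The result rests on an unadjusted two-sample comparison, the alpha given in the general sections, and no attrition; the plan's own attrition rate lowers it only to about 96.5%. No stated input accounts for the gap.

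This is a reporting error in the conservative direction. It should be corrected because it concerns the only primary endpoint, but it does not call the design into question.

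**What to change.** In SAP 3.7 and protocol 9.2, replace the power sentence with one of two equivalent statements, naming the alpha:

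- about 97% power to detect 0.22% with SD 1.1%, at two-sided 0.05 (one-sided 0.025); or
- 90% power to detect about 0.19% with SD 1.1%, at the same level.

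If the 90% did come from an unreported SD or missing-data allowance, the sponsor should state that input with its source. The 1.30% and 28% above are back-calculated and should not be inserted to preserve the figure: an SD of 1.30% would sit beside 1.1% for the same variable in the insulin subset, and a 28% allowance would contradict the use of values from all subjects.

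The cost is one sentence in each document. The SAP can be corrected directly, with a line in SAP section 12 (changes from the protocol). The protocol sentence can wait for an amendment made for other reasons. The sample size, event target and analyses do not change.
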